1. AMENDMENTS FROM PREVIOUS VERSION(S)

None.

2. GLOSSARY OF ABBREVIATIONS

AE	Adverse Event
GCP	Good Clinical Practice
ICH	International Conference on Harmonisation
IMP	Investigational Medicinal Product
BASEC	Begleitete Dokumentation von klinischen Studien (“Accompanied documentation of clinical studies”)

3. INTRODUCTION

*Understanding the neurodynamics of emotional and behavioral states through pharmacological stimulation with psychoactive compounds that modulate specific neurotransmitter systems in the brain represents a current research priority in cognitive and affective neuroscience. The endogenous neurotransmitter serotonin (5-hydroxytryptamine, 5-HT) seems to be crucially involved in the regulation of mood and social cognition. Hence, serotonergic psychoactive compounds have been used to investigate the pharmacological underpinnings of emotional processing, social cognition and empathy in human subjects. Psilocybin, LSD, DMT and MDMA provide valuable tool compounds for the safe investigation of serotonergic neurotransmission, brain function and the association of these neural changes with emotional and cognitive states (1-3). In recent years, psychedelic compounds such as psilocybin, LSD, ayahuasca and the dissociative anesthetic ketamine have been used in clinical and non-clinical trials to investigate the underlying neural mechanisms of action and to explore their efficacy in the treatment of affective disorders such as major depressive disorder (MDD), anxiety disorders, substance use disorders (SUD), and post-traumatic stress disorder (PTSD) (2, 4, 5). As a 5-HT2A-receptor agonist, DMT needs to cross the blood-brain-barrier (BBB) in order to evoke its psychotropic effects on the human psyche. This is achieved by parenteral administration either via smoking/vaping the substance, or by direct intravenous administration into the blood stream (6-8). However, DMT is not able to evoke noticeable effects by stand-alone oral administration (8, 9). This is due to the intense first pass-effect occurring in the gastro-intestinal tract by monoamine oxidase (MAO) (8). Urine analysis after intravenous administration of DMT to volunteers yielded indole-3-acetic acid (IAA) as the main metabolite of DMT, which is the oxidative deamination product of the examined drug (6). Further evidence for the involvement of MAO in the metabolism of DMT is given by the pharmacology of ayahuasca, as the traditional brew consists also of *Banisteriopsis caapi*, the ayahuasca vine that contains high concentrations of the β -carboline alkaloids harmin, harmaline, and tetra-hydroharmine. All of those alkaloids were shown to be reversible MAO-A inhibitors and are necessary to facilitate the psychoactive effects of ayahuasca (10-13). MAO however, is not the only enzyme metabolizing DMT in the human body, as urine samples were found to contain DMT-N-oxide (DMT-NO) in significant concentrations, besides DMT and IAA (14). When DMT is administered alone, urine analysis 24h after intake resulted in a composition of DMT and its two main metabolites DMT-NO and IAA in a ratio of 0.04%, 3.05% and 96.91% respectively (8).*

The goal of this clinical trial is to compare corresponding inter- and intraindividual pharmacokinetic and pharmacodynamic profiles of DMT and the MAO-A inhibitor harmine, including assessments of safety & tolerability.

3.1. Study Design

This is a single-blind, randomized, two-arm, dose-response study of DMT and harmine in healthy subjects.

N = 16 healthy female and male subjects (25-45 y) with no current or previous history of neurological or psychiatric disorder and no first-degree relatives with history of Axis-I psychiatric disorder will be recruited by medical screening. In this open-label pilot study, acute subjective effects and blood samples following the administration of escalating doses of DMT and harmine as a sublingual single preparation are measured. Additionally, on the fourth test day participants will receive either DMT or harmine only as a sublingual preparation according to their arm allocation. The study will be conducted at the Psychiatric University Hospital Zurich (PUK). Study participants will undergo a telephone and medical screening before enrolment to the study. Possible doses for each study day are given in section 3.4. Blood sampling and pharmacokinetic modeling, as well as assessing vital signs and the intensity of subjective effects follows the timeline shown in the figure below. Blood is sampled 15 times over the course of 24 h. Vital signs and the intensity of subjective effects will be monitored throughout the study at baseline, 0, 20, 40, 60, 85, 120, 150, 180, 240, 300, 540, 1440 (= 24h) after administration. This protocol is used for all 6 pilot days. ECG is measured

at baseline, 75, 150, 300, 540, and 1440 min after administration. Body temperature is measured at baseline, 75, 180, 300, 540, and 1440 min after administration. Semistructured interviews will be conducted on the second study day towards the end of the study day. The 'Aliveness' Task will be conducted on the first 3 study days at ~100 min after substance administration. Participants will be released at the end of the study day but will come back the following day for their assessments 24 hours after first substance administration.

The daily schedule for study events are displayed in Figure 3. A detailed description of the schedule for the study participation and procedures is provided in the accompanying protocol (BASEC-Nr. 2022-00973).

3.1.1. Initial titration period

We will administer the sublingual formulation with varying fixed starting doses of DMT and harmine and let the study participants increase the total dose of DMT and harmine in 20 minute intervals at fixed increments up to two times. We will test 7 different dosing conditions with varying DMT:harmine ratios during the first 4 days (see figure 1). The tested ratios range between 0-120 mg DMT and 0-180 mg harmine. The dose ratios will be administered in a sequential order with two different sequences in two arms, and the DMT or harmine only condition will be tested on the fourth study day; this is done to further clarify if DMT alone is capable of inducing its effects with routes other than intravenous administration or inhalation. The DMT/harmine only condition is the only one that is exclusive for one of the two study arms. The rationale behind this dosing scheme is to find the optimal dose of harmine and DMT independently of each other by taking account for order/PD habituation and linear/non-linear drug-drug-interaction effects and to establish the optimal dosing for the future studies based on PK/PD analytics.

3.1.2. Non-identical cross-over period

A non-identical cross-over paradigm will be applied on days 5 and 6. This scheme will allow us to explore DMT/harmine in additional combinations which were explored in the initial titration phase so that all individuals in both treatment arms have been exposed to all combinations, except for the DMT-only and Harmine-only conditions which are unique to each arm. The timeline for this study is shown in figure 2.

[figure not shown]

Figure 1. Dose ratios for the dose-finding study. The sublingual formulation is administered in a ratio-varying manner on six study days in two arms that differ in the order of substance administrations (equivalent to a cross-over design). On the 4th study day, participants will either receive DMT or harmine only, depending on the arm they are allocated to.

RE01 - DHTP - Statistical Analysis Plan

[figure not shown]

Figure 2. Study flow chart for the dose-finding study.

[figure not shown]

Figure 3. Timeline of drug administration and assessments for each study day.

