7.4.7. ECG Data

Absolute values and changes from baseline in QT, heart rate, QTcF, PR and QRS will be summarized by dose combination and time post-dose using sponsor reporting standards. Tables will be paged by parameter. Baseline is as defined in Section 5.

Mean changes from baseline in QT, heart rate and QTcF will be plotted against time post-dose. On each plot there will be 1 line for each treatment. Data from all dose combinations will be plotted on the same figure using separate lines for different dose combinations. Corresponding individual plots of changes from baseline will also be produced for each dose combination.

Changes from baseline in QTcF will also be plotted separately against drug concentrations. This will be a scatter plot for all observations where QTcF and drug concentration are recorded. Different symbols will be used for each treatment.

Maximum increase from baseline for QTcF, heart rate, QT, PR and QRS will be summarized by dose combination, according to sponsor reporting standards.

In addition, for QTcF, heart rate and QT, the differences between each dose combination (dose combination 1 – dose combination 2) for each subject will be summarized and plotted (N, mean, 95% confidence interval) for dose combination and timepoint (including baseline).

ECG endpoints and changes from baseline (QTcF, PR and QRS) will also be summarized descriptively by dose combination using categories as defined in Section 8.1 (for QTc these correspond to ICH E14¹). Numbers and percentages of subjects meeting the categorical criteria will be provided. All planned and unplanned post-dose timepoints will be counted in these categorical summaries. All values meeting the criteria of potential clinical concern will be listed.

Listings of subjects with any single post-dose value ≥ 500 msec will also be produced for QTcF.

QTcB will be listed only and not summarized.

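### Both single-drug conditions are given only on day 4, when no combination is given, so single-drug versus combination differences cannot be separated from order without an assumed day trend

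*SAP*

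**What the plan says.** Section 3.1.1 (Initial titration period) sets out the conditions and their order: "We will test 7 different dosing conditions with varying DMT:harmine ratios during the first 4 days", and "The dose ratios will be administered in a sequential order with two different sequences in two arms". It fixes the place of the single-drug conditions: "the DMT or harmine only condition will be tested on the fourth study day". It says the scheme finds the optimal doses "by taking account for order/PD habituation and linear/non-linear drug-drug-interaction effects".

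In Section 3.1.2, the Figure 1 caption refers to "two arms that differ in the order of substance administrations (equivalent to a cross-over design") and then adds: "On the 4th study day, participants will either receive DMT or harmine only, depending on the arm they are allocated to". The text of 3.1.2 says that days 5 and 6 complete the exposure of both arms to every combination, "except for the DMT-only and Harmine-only conditions which are unique to each arm".

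On analysis, Section 7.4.7 (ECG Data) plans that differences between dose combinations "for each subject will be summarized and plotted (N, mean, 95% confidence interval"). Section 7.3.1.1 plans a conditional mixed-effects model for AUC and Cmax over all administered dose combinations. Section 3.2 (Statistical Decision Rules) names subjective effects and DMT AUC as dependent variables. None of these places mentions a study-day or period term.

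**The concern.** DMT-only and harmine-only are the zero-dose margins of the drug-drug interaction that Section 3.1.1 says the scheme handles. Each subject reaches a single-drug condition after three earlier active sessions, and never on another day. A weaker response on day 4 could therefore reflect the absent partner drug, or simply the fourth session. The SAP itself names habituation as something to account for.

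The SAP discloses that each single-drug condition belongs to one arm. It does not say what follows from both being tied to the same day. A reader of the ECG differences with 95% confidence intervals, or of a mixed model over all conditions, could take a day effect for a drug effect while being told that order had been dealt with. An analyst who adds day as a factor would lose the contrast altogether.

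**Working it through.** **Inputs, all from Sections 3.1.1 and 3.1.2.** Two arms with one sequence each; six study days; seven conditions in the first four days; one single-drug condition per arm, on day 4; every combination received by both arms by day 6. Figure 1 is not shown, so the exact orders are unknown.

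**Reproducing the count of seven.** Each arm has three combination days (1–3) before day 4. With s combinations shared between the arms in that period, the number of conditions is 3 + 3 − s + 2 = 7, so s = 1. That leaves 5 combinations and 2 single-drug conditions. Each subject receives 5 + 1 = 6 conditions over six days, which agrees with the text.

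**Pairs of conditions.** 7 × 6 / 2 = 21 pairs:
- 10 combination–combination pairs, received by both arms;
- 10 single-drug–combination pairs, each available within subject in one arm only (about 8 of 16 subjects if allocation is equal, which is an assumption);
- 1 pair, DMT-only versus harmine-only, which no subject receives in full.

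**Identity.** On day 4 every subject receives a single drug, and on no other day does anyone. So the indicator of day 4 equals the indicator of DMT-only plus the indicator of harmine-only. In a model with subject, day (factor) and condition, add any constant δ to the day-4 effect and subtract δ from both single-drug effects: every fitted cell mean is unchanged. Single drug minus combination changes by δ, so it is not estimable. DMT-only minus harmine-only does not change.

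**Check over the possible orders.** The orders consistent with the text number 6 × 2 × 3 × 6 × 2 = 432: arm A days 1–3, arm A days 5–6, choice of the shared combination, arm B days 1–3, arm B days 5–6. A rank test of each contrast gave:
- day as factor, any single-drug versus combination contrast estimable: 0 of 432;
- day as factor, DMT-only versus harmine-only estimable: 432 of 432;
- day as factor, all ten combination–combination contrasts estimable: 144 of 432;
- linear day term, all single-drug versus combination contrasts estimable: 432 of 432.

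With the linear term, and 8 subjects per arm assumed, the variance of single drug versus the mean of the combinations rises by a factor of 1.009 to 1.017.

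**Bias if day is ignored.** Assume a linear drift of b per study day. The bias of single drug minus a combination given on day d is (4 − d)b:

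| d | 1 | 2 | 3 | 5 | 6 |
|---|---|---|---|---|---|
| bias | +3b | +2b | +b | −b | −2b |

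Against the mean of the five combinations, the mean day is (1 + 2 + 3 + 5 + 6)/5 = 3.4, so the bias is (4 − 3.4)b = 0.6b. The other arm cannot average this out, because each single drug occurs in one arm only.

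**The case against.** The strongest reply is that the SAP is open about the layout and modest about the analysis. Section 3.1.2 is titled as a non-identical cross-over and exempts the single-drug conditions. The analysis is descriptive. The purpose given for the mixed model is to estimate intra-subject variation. The one reason given for the single-drug day is whether DMT alone acts by this route, which can be read from DMT-only change from same-day baseline without any combination contrast. All of this stands. It limits the weight of the point but does not make the order statement true for these conditions. A reader might infer that measuring what harmine adds is the stated reason for day 4; Section 3.1.1 does not say so.

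It can also be said that Section 7.4.7 speaks of dose combinations and may not mean the single drugs. The wording is unclear. But PK, safety and ECG results are organised by dose combination throughout Section 7, so a strict reading would leave the single-drug conditions without a planned summary there.

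Finally, combinations on days 1–3 and 5–6 lie on both sides of day 4, so a smooth trend would allow an adjusted comparison. That is correct, but the SAP specifies none.

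**Conclusion.** The point holds. The order and cross-over statements claim a property that the design lacks for DMT-only and harmine-only, and this does not depend on the missing figure. The non-estimability is exact when day is an unrestricted factor. The size of any bias is not known: +3b to −2b per pair, and 0.6b against the mean of the combinations, rest on an assumed linear drift whose b the SAP does not give. Drift is most plausible for subjective effects and vital signs; for PK it is only an assumption.

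Three stronger readings are tempting and not supported:
- That the single-drug data cannot be compared with the combinations at all. With a stated linear trend they can, in every order consistent with the text.
- That the cross-over claim is safe for the five combinations. With day as a factor, all ten of their contrasts are estimable in only one third of the possible orders, so this depends on Figure 1.
- That the day-4 comparison between arms is free of order. It is randomised and made on the same day, but the arms followed different sequences on days 1–3.

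The point merits correction before analysis. The analyses are mainly descriptive, and the primary objective of safety and tolerability does not turn on it.

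**What to change.** 1. In Section 3.1.1 and the Figure 1 caption, withdraw the order and cross-over statements for the single-drug conditions and state that single-drug versus combination comparisons are not separable from day 4. Keep the statements for combination pairs only where the Figure 1 sequences make the contrast estimable with day in the model.
2. In Sections 7.3.1.1 and 7.4.7, say whether dose combination includes the single-drug conditions. Keep the descriptive differences, but label single-drug versus combination ones as confounded with day. Add a sensitivity estimate from a mixed model with a linear study-day term, whose slope comes from combinations given on different days in the two arms. State that it depends on linearity, and that a categorical day term would make the contrast non-estimable.
3. Optionally, report the day-4 difference between arms, DMT-only versus harmine-only, in change from same-day baseline. Describe it as randomised and same-day, but not free of the arms' different sequences on days 1–3.

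The cost is SAP wording and a few extra tables from data already planned, a more modest claim for the single-drug comparisons, and an openly stated linearity assumption. No dosing or schedule change is proposed.

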2.2 Study Objectives

2.2.1 Primary Objective

- To determine the safety and tolerability of various dose combinations of a DMT/harmine formulation in healthy subjects.

2.2.2 Secondary Objectives

- To characterize the PK of DMT in plasma and urine following oral administration of escalating single oral doses to healthy subjects.
- To characterize the PK of harmine in plasma and urine following oral administration of escalating single oral doses to healthy subjects.

2.2.3 [REDACTED]

CC1

3. HYPOTHESES AND DECISION RULES

3.1. Statistical Hypotheses

No formal statistical tests are anticipated, unless adequate conditions for within-subject analyses are met.

3.2. Statistical Decision Rules

If protocol adherence is sufficient for within-subject statistical tests to be valid and the collected data from the study prove suitable for such analysis, a mixed-effects model would be applied. This model would utilize subjective effects and DMT AUC as dependent variables.

4. ANALYSIS SETS

4.1. Full Analysis Set

In general, the full analysis set is composed of all randomized subjects, following the intention-to-treat (ITT) principle. The ITT principle includes all subjects in the analysis based on their randomized treatment assignment, regardless of whether they received the treatment, completed the study, or adhered to the protocol. Analysis sets for PK, pharmacodynamic, safety, and the highest dose condition data are defined in Sections 4.2, 4.3, 4.4, and 4.5.

4.2. Pharmacokinetic Analysis Set

4.2.1. Concentration Analysis Set

The PK concentration population is defined as subjects treated who were administered all three doses for at least one dose condition.

4.2.2. Parameter Analysis Set

The PK parameter population is defined as subjects treated who were administered all three doses and have at least one of the PK parameters of interest for at least one dose condition.

4.3. Pharmacodynamic Analysis Set

The pharmacodynamic analysis population is defined as subjects who were administered all three doses and have at least one of the pharmacodynamic parameters of interest for at least one dose condition.

4.4. Dose Interruption Analysis Set

The Dose Interruption population is defined as subjects treated who were administered two out of the three doses per dose combination.

4.4.1. Pharmacokinetic Analysis Set

4.4.1.1 Concentration Analysis Set

The Dose Interruption PK concentration population is defined as subjects treated who were administered only two doses for at least one dose combination.

4.4.1.2 Parameter Analysis Set

The Dose Interruption PK parameter population is defined as subjects treated who were administered only two doses for at least one dose combination and have at least one of the PK parameters of interest.

4.4.2. Pharmacodynamic Analysis Set

The Dose Interruption pharmacodynamic population is defined as subjects treated who were administered only two doses for at least one dose combination and have at least one of the pharmacodynamic parameters of interest.

4.5. Safety Analysis Set

Subjects who receive at least one dose of study medication for any dose combination will be included in the safety analyses and listings.

4.6. Treatment Misallocations

All analyses will be performed as “per protocol” and will not include data from subjects who are randomized but not treated.

If a subject takes a treatment that is not consistent with the treatment they are randomized to, for example takes a treatment out of sequence or takes the same treatment twice, then they will be reported under the treatment that they received for all safety, PK and pharmacodynamic analyses, where applicable.

4.7. Protocol Deviations

Subjects who experience events that may affect their PK profile (e.g., vomiting) may be excluded from the PK analysis if a clear rationale thereof is documented. At the discretion of the pharmacokineticist a concentration value may also be excluded if the deviation in sampling time is of sufficient concern or if the concentration is anomalous for any other reason.

A full list of protocol deviations will be compiled and reviewed to identify major and minor deviations prior to database closure.

4.7.1. Deviations Assessed Prior to Randomization

At screening, the investigator will assess subjects against the inclusion and exclusion criteria as set out in Sections 4.1 – Section 4.2 of the protocol.

4.7.2. Deviations Assessed Post-Randomization

Any significant deviation from the protocol will be reviewed prior to database closure and a decision taken regarding evaluation for each analysis population.

5. ENDPOINTS AND COVARIATES

Subjects who receive at least one dose of randomized study IMP and have a baseline and at least one post-baseline measurement (after taking randomized study medication) will be included in the data analyses. Baseline is defined as the last pre-dose measurement from each measurement day.

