5.1. Primary Endpoint(s)

- Pharmacokinetic parameter "Cmax": Dose-dependent changes in Cmax of several doses of combined DMT & Harmine.
- Pharmacokinetic parameter "Area under the curve (AUC)": Dose-dependent changes in AUC of several doses of combined DMT & Harmine.
- Pharmacokinetic parameter "T1/2": Dose-dependent changes in T1/2 of several doses of combined DMT & Harmine.
- Incidence of Treatment-Emergent Adverse Events: Dose-dependent changes in incidence of adverse drug reactions.
- Blood count (Lab biochemistry): Changes from baseline in blood count.
- Clinical chemistry (Lab biochemistry): Changes from baseline in any clinical chemistry parameter with potential clinical relevance.
- Blood coagulation (Lab biochemistry): Changes from baseline in blood coagulation.
- QT interval (12-lead Electrocardiogram [ECG]): Dose-dependent changes of QT intervals assessed by clinical 12-lead ECG).
- Blood pressure: Dose-dependent changes in systolic and diastolic blood pressure.
- Heart rate: Dose-dependent changes in heart rate.

- Temperature: Dose-dependent changes in body temperature (in °C).
- Genotyping: Collection of saliva-samples to determine genetic polymorphisms.
- Subjective effects: Dose-dependent changes in trajectories of subjective effects.

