5.4.2. Laboratory Safety Tests

Safety laboratory tests will be performed as described in the protocol.

To determine if there are any clinically significant laboratory abnormalities, the haematological, clinical chemistry (serum) safety tests will be assessed against the criteria specified in the sponsor reporting standards. The assessment will consider whether each subject's baseline test result is within or outside the laboratory reference range for the particular laboratory parameter.

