7.4.5. Laboratory Data

Laboratory data will be listed and summarized by treatment in accordance with the sponsor reporting standards.

Mean change from baseline will be plotted against nominal time post dose. On each plot there will be one line for each treatment. Individual plots of changes from baseline will also be produced for each dose combination and total doses per dose combination.

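### The only baseline rule is the same-day pre-dose value, so for laboratory endpoints the day 2 to 6 baselines are post-exposure values and any change that persists between study days drops out of the change-from-baseline summaries

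*SAP*

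**What the plan says.** Section 5 of the SAP, in the general paragraph that opens the endpoint chapter, states: "Baseline is defined as the last pre-dose measurement from each measurement day". The sentence is not limited to any endpoint. Sections 7.4.6 (vital signs) and 7.4.7 (ECG) refer back to it. Section 7.4.5 (laboratory data) uses change from baseline without a definition of its own, and the SAP contains no other baseline definition.

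Three laboratory endpoints in Section 5.1 depend on it:
- "Blood count (Lab biochemistry): Changes from baseline in blood count"
- For clinical chemistry: "Changes from baseline in any clinical chemistry parameter with potential clinical relevance"
- "Blood coagulation (Lab biochemistry): Changes from baseline in blood coagulation"

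Baseline also enters the search for clinically significant abnormalities in Section 5.4.2: "The assessment will consider whether each subject's baseline test result is within or outside the laboratory reference range for the particular laboratory parameter".

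For display, Section 7.4.5 says: "Mean change from baseline will be plotted against nominal time post dose". These plots have one line per treatment, with individual plots per dose combination and number of doses. No laboratory display by study day is planned.

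On exposure, the caption of Figure 1 in Section 3.1.2 reads: "The sublingual formulation is administered in a ratio-varying manner on six study days in two arms". Section 3.1.1 says that the two arms receive the combinations in different sequences.

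**The concern.** A same-day baseline isolates the acute response to that day's combination. It is a sound reference for measures that return to their resting level between sessions. A blood count, liver enzyme or coagulation value need not do so. If part of a shift is still present at the next session, it becomes part of that day's baseline and is subtracted.

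Two outputs are affected. The change-from-baseline summaries and plots would show only each day's increment, never the accumulated change since before the first dose. In Section 5.4.2, a result pushed out of range by earlier sessions could be read on later days as a subject who started that day abnormal. Safety and tolerability is the primary objective (Section 2.2.1), and nothing else in the plan measures laboratory change from an unexposed state.

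**Working it through.** The SAP states no figure on this point, so there is nothing to reproduce. The check is an illustration of what the definition does.

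**Inputs**
- From the SAP: six study days (Section 3.1.2); same-day pre-dose baseline (Section 5).
- Assumed: each exposure shifts a laboratory value by *d*, visible in that day's post-dose sample, and a fraction *f* of the accumulated shift is still present before dosing on the next study day. The SAP gives no information on *f*, so the full range 0 to 1 is shown.

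**Formulas**
- Pre-dose shift on day *k*: d(f + f² + … + f^(k−1)).
- Day-6 post-dose change from the day-1 pre-dose value: C = d(1 + f + f² + f³ + f⁴ + f⁵).
- Day-6 change from the same-day baseline: *d*, whatever *f* is.
- Share removed: 1 − d/C.

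| f | C | Same-day change | Share removed |
|---|---|---|---|
| 0 | 1.00d | 1.00d | 0% |
| 0.25 | 1.33d | 1.00d | 25% |
| 0.5 | 1.97d | 1.00d | 49% |
| 0.75 | 3.29d | 1.00d | 70% |
| 1 | 6.00d | 1.00d | 83% (5/6) |

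**Effect on the in/out-of-range assessment.** Assumed example: start at 25 U/L, d = 6, upper limit 40.

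With full carry-over (f = 1), pre-dose to post-dose values are:
- day 1: 25 to 31
- day 2: 31 to 37
- day 3: 37 to 43
- day 4: 43 to 49
- day 5: 49 to 55
- day 6: 55 to 61

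The change since before the first dose is 61 − 25 = +36. The same-day change is +6 on every day. The first out-of-range value is on day 3, against an in-range baseline of 37. On days 4 to 6 the baseline itself is out of range (43, 49, 55), although the subject started at 25.

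With f = 0.75 in the same example:
- Day-4 pre-dose is 25 + 6 × (0.75 + 0.5625 + 0.4219) = 35.4, and post-dose is 41.4, which is the first crossing.
- Day-6 pre-dose is 25 + 6 × 2.288 = 38.7, still in range.

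Here no baseline is reclassified. Reclassification is therefore possible but not certain: it needs strong carry-over or a starting value near the limit.

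**The case against.** The case against has real weight.

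- **The same-day baseline answers the plan's main question.** Section 7.4 evaluates each dose combination, and the laboratory plots are by treatment. For contrasts between combinations given to the same subjects on different days, a period baseline is a recognised choice. This stands. Replacing it by a day-1 baseline in those plots would charge the effects of earlier combinations to later ones. The pre-first-dose reference should be added to it, not substituted for it.
- **Carry-over is assumed.** No section says that laboratory effects last between study days, and the SAP text does not give the interval. This stands, and it is why only a range can be given. With f = 0 the two baselines agree.
- **Other outputs remain.** Laboratory data are also listed and summarized by treatment. Section 5.4.2 says only that baseline status is considered, not that results with an abnormal baseline are set aside. This stands too. However, summaries by treatment pool earlier and later study days across two sequences, so they do not show drift clearly.
- **The rule might be meant only for vital signs and ECG,** because only those sections refer back to it. This does not stand: the Section 5 sentence is general, and nothing else defines a laboratory baseline.

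A reader might go further and infer that the plan would report no laboratory change when one occurred. The documents do not support that: in the example the same-day change is +6 every day, and the first crossing appears against a normal baseline. Only an effect that emerges after each day's last sample would escape the same-day change altogether, and the sampling times are not in the SAP.

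A reader might also infer, from the urine tests listed under baseline in Section 7.4.10, that no pre-dose laboratory baseline exists. That table covers screening and special-purpose data. It is not the safety-laboratory schedule, which Sections 5.4 and 5.4.2 leave to the protocol.

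Finally, Section 2.2.1 speaks of various dose combinations. It does not make cumulative toxicity of repeated dosing the stated objective.

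**Conclusion.** The point holds as a gap in the laboratory baseline definition. As written, the reference value for blood count, clinical chemistry and coagulation on days 2 to 6 is a post-exposure value, and no display is made against an unexposed value or by study day. The change-from-baseline summaries lose 0% to 83% of the accumulated day-6 change as assumed carry-over goes from none to full. This rests on a constant shift per exposure that is visible on the same day and on a constant retained fraction, neither of which comes from the SAP. An out-of-range value from earlier sessions can also be treated as an abnormal baseline on later days in Section 5.4.2. The actual size cannot be computed from the SAP and may be zero. The planned outputs do not conceal every laboratory effect, but they are not set up to show one that accumulates.

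**What to change.** 1. **Section 5:** keep the same-day pre-dose baseline for vital signs, ECG and subjective effects, and for the laboratory plots by dose combination.
2. **Section 5:** for blood count, clinical chemistry and coagulation, also define a pre-first-dose baseline as the last value before the first study dose. Confirm against the protocol which sample supplies it. Section 7.4.10 lists chemistry at screening but does not mention blood count or coagulation there.
3. **Section 5.4.2:** use the pre-first-dose baseline to decide whether a subject's baseline is inside or outside the reference range.
4. **Section 7.4.5:** add a supplementary summary and plot of change from the pre-first-dose baseline by study day.

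The cost is SAP wording, one derived variable and one extra display. No samples are added. The downside is that the cumulative display mixes combination with study day. The SAP should say that it is not to be used to attribute an effect to a single combination.
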